- The subject is receiving antibacterial therapy that may be effective for the infection under study for a different infection from the 1 under study.
- Discontinued study therapy due to an AE prior to Early Clinical Response assessment.
- Death prior to the Early Clinical Response assessment.

Indeterminate: the clinical response to test article could not be adequately inferred due to:

- Subjects were not seen for the evaluation because they withdrew consent, were lost to follow-up, other reason (specify).
- Other specified reason.

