In iv studies in healthy subjects, modest and reversible alanine aminotransferase (ALT) increases were seen most notably with iv doses of 300 mg or greater (3 × higher than the therapeutic dose of 100 mg iv). There were no differences in ALT changes in the Phase 2 study compared to linezolid. Transient increases in heart rate were observed following administration of single and multiple doses of omadacycline, with a dose dependent mean increase of up to 15-20 beats per minute (bpm) compared to placebo for the first 4 hours after dosing. The increases in heart rate were not reported as AEs and not associated with any other cardiac findings. These increases were observed most consistently during the 2 hours immediately post-infusion. Beyond 6 hours after the start of the infusion, heart rate in all subjects, including controls, were comparable. A listing of all Phase 1 AEs is provided in Appendix I of the IB ([Paratek, 2014](#)).

In the Phase 2 study, omadacycline was well-tolerated. The most frequently reported AEs were GI-related occurring in 21 (18.9%) of 111 omadacycline-treated, and 18 (16.7%) of 108 linezolid-treated subjects. Nausea and vomiting were reported in 11 (9.9%) and 5 (4.5%), respectively, of omadacycline-treated subjects primarily during po treatment, compared to 8 (7.4%) and 4 (3.7%), respectively, of linezolid-treated subjects. Premature discontinuation of treatment due to an AE was very infrequent, occurring in 0.9% and 1.9% of omadacycline and linezolid-treated subjects, respectively.

There was no pattern of adverse changes in laboratory safety parameters among subjects treated with omadacycline or linezolid; changes in omadacycline-treated subjects were comparable to those observed with linezolid. In particular, there was no clinical or statistical difference between the treatment groups in ALT values or in other liver function tests (LFTs).

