- The subject is receiving antibacterial therapy that may be effective for the infection under study for a different infection from the 1 under study.
- Discontinued study therapy due to an AE and received alternative antibacterial treatment for CABP prior to the Early Clinical Response assessment.,
- Death prior to the Early Clinical Response assessment.

Indeterminate: the clinical response to test article could not be adequately inferred due to:

- Subject was not seen for the evaluation because they withdrew consent, were lost to follow-up, other reason (specify).
- Other specified reason.

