22.15 Handling of Missing Values/Censoring/Discontinuations

Missing values will not be imputed for primary and secondary efficacy and safety analyses (except as detailed in the SAP for missing dates) and only observed values will be used in data analyses and presentations. For the primary outcome measure, if any data field needed to determine the response is missing the subject will be assigned an Indeterminate response. Subjects with an Indeterminate response are included in the denominator, and thus, are

considered Clinical Failures. A sensitivity analysis of the primary outcome will be conducted in which subjects with an Indeterminate response are considered Clinical Successes.

For the secondary outcome measure of Investigator's Assessment of Clinical Response at PTE in the ITT population (co-primary for EMA analysis), subjects with missing data are assigned an Indeterminate response. Subjects with an Indeterminate response are included in the denominator, and thus, are considered failures. Table 9 provides a summary of the handling of missing/indeterminate outcomes for the Investigator's Assessment of Clinical Response at PTE.

Table 9 Investigator's Assessment of Clinical Response at PTE Determination Given Missing Data

EOT Visit	PTE Visit	Overall Assessment of Clinical Response at PTE (Investigator's Assessment)
Missing/indeterminate	Success	Indeterminate
Missing/indeterminate	Failure	Failure
Missing/indeterminate	Missing/indeterminate	Indeterminate
Success	Missing/indeterminate	Indeterminate
Failure	Missing/indeterminate	Failure

For the analysis in the ITT analysis set of Investigator's Assessment of Clinical Response at PTE, Indeterminate outcomes are included in the denominator and are thus considered Clinical Failures.

Missing data are handled in a similar manner for the outcome of microbiological response at PTE.

EOT = end of treatment; ITT = intent-to-treat; PTE = post-therapy evaluation.

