Clinical Success: survival with improvement of at least 1 level (ie, severe to moderate, moderate to mild, mild to absent) compared to baseline (Screening) in at least 2 CABP symptoms (cough, sputum production, pleuritic chest pain, and dyspnea) with no worsening by at least 1 level in the other CABP symptoms. In order for the subject to be considered a Clinical Success, the subject may not meet any criteria for Clinical Failure or Indeterminate Early Clinical Response.

Clinical Failure: meeting any of the following criteria:

- There is no improvement by at least 1 level (ie, severe to moderate, moderate to mild, mild to absent) compared to baseline (Screening) in 2 CABP symptoms.

- Any of the 4 CABP symptoms is worse (by at least 1 level) compared to baseline (Screening).
- The subject requires alternative (rescue) antibacterial treatment for CABP prior to the Early Clinical Response assessment related to either (a) progression or development of new symptoms attributable to CABP or (b) development of infectious complications of CABP (eg, empyema, lung abscess).
- The subject is receiving antibacterial therapy that may be effective for the infection under study for a different infection from the one under study.
- Discontinued study therapy due to an AE prior to the Early Clinical Response assessment.
- Death prior to the Early Clinical Response assessment.

Indeterminate: the clinical response to test article could not be adequately inferred due to:

- Subject was not seen for the evaluation because s/he withdrew consent, were lost to follow-up, other reason (specify).
- Other specified reason.

Subjects with missing data such that an Early Clinical Response cannot be determined will be considered an indeterminate response. Subjects who did not have at least 2 symptoms of CABP at baseline will also be considered an indeterminate response. Since subjects with an indeterminate response are included in the denominator of the calculation of Clinical Success, these subjects are essentially Clinical Failures. For the ITT population, the proportion of ITT subjects with a Clinical Success is defined using the following formula:

$$\frac{\text{Number of subjects with an Early Clinical Success}}{\text{Number of subjects with an Early Clinical Failure} + \text{Number of subjects with a response of Indeterminate} + \text{Number of subjects with an Early Clinical Success}}$$

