7 CHANGES IN CONDUCT OR PLANNED ANALYSES FROM THE PROTOCOL

The expanded microITT population was added and selected analyses are conducted in this population.

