8.3 Handling of Missing Data

Missing data will be handled as outlined below:

- All missing and partial dates for adverse events or for medications received after randomization will be queried for a value. If no value can be obtained, substitutions will be made as detailed in [Appendix 3](#). These substitutions will be used in calculations; however, the actual value recorded on the eCRF will be used in all listings.
- Missing start and stop times for prior and concomitant antibiotics will be queried for a value. If no value can be obtained but the site indicates the antibiotic was received (onset time) prior to the first dose of test article, 00:01 will be used for the onset time. If the site also indicates that the end time was prior to the first dose of test article, 00:01 will be used for end time. The actual value (blank) will be recorded on the eCRF and will be used in the listings.
- Missing times for assessments of CABP symptoms will be queried for a value. If minutes are not available, the time will be recorded to the closest hour.
- If no value can be obtained for all other times for events and assessments occurring after randomization, the time will not be imputed but will remain missing.
- The severity and causality assessment for adverse events cannot be missing. Missing data will be queried for a value.

For clinical and microbiological response, missing data will be handled as follows:

- For the primary outcome measure (Early Clinical Response at 72 to 120 hours after administration of the first dose of test article):
 - The subject will be considered to have missing data if an assessment of all of the CABP symptoms (cough, sputum production, pleuritic chest pain, and dyspnea) is not made from 72 to 120 hours after the administration of the first dose of test article, unless the subject is considered a Clinical Failure for another reason. Subjects who do not have at least 2 symptoms of CABP at baseline will also be considered to have missing data unless the subject is considered a Clinical Failure for another reason. Subjects with missing data will be defined as an Indeterminate response which is essentially a Clinical Failure for the primary analysis in the ITT population.

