10.2 Sensitivity and Additional Analyses of the Primary Efficacy Outcome

If the null hypothesis of inferiority is rejected for Early Clinical Response in the ITT population and the observed success response proportion for omadacycline is larger than the observed proportion for moxifloxacin, a formal statistical analysis of superiority will be conducted. If the lower limit of the 95% 2-sided CI for the treatment difference is greater than 0.00, omadacycline will be considered superior to moxifloxacin.

Sensitivity analyses of the primary outcome include:

- Determination of the 95% CI adjusted for PORT Risk Class (II vs III/IV), prior use of antibiotics (yes and no), and geographic region (Western Europe/North America, Eastern Europe, and Rest of World). If there are < 20 subjects within a stratum and treatment group or there is a 0 count within a stratum for a treatment group and outcome, the geographic regions of Eastern Europe and Rest of World will be combined. If the combining of the geographic regions is not sufficient to complete the adjusted analysis,

receipt of prior antibiotics (yes vs no) will be combined. The 95% CI interval will be computed using the stratified methodology of Miettinen and Nurminen ([1985](#)). Cochran-Mantel-Haenszel weights will be used for the stratum weights in the calculation of the CI as follows, where n_{1i} = number of subjects in Group 1 in the i th stratum; n_{2i} = number of subjects in Group 2 in the i th stratum:

$$W_i = \frac{n_{1i}n_{2i}}{n_{1i} + n_{2i}}$$

- The second sensitivity analysis of the primary outcome will consider all subjects who are lost to follow up prior to having an Early Clinical Assessment or have missing data, as an Early Clinical Success (these subjects are considered Indeterminates and analyzed as Clinical Failures in the primary analysis).

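### The SAP and the current protocol define failure on the primary endpoint differently for subjects who stop for an adverse event, and the SAP does not declare the difference

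*Combined protocol and SAP*

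**What the plan says.** Early Clinical Response at 72 to 120 hours is derived by program from the investigator's symptom scores. In both documents a subject who meets any failure criterion cannot be a Success. The documents differ on one criterion:

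- **SAP 5.2.1** (Final 1.0, 17-MAR-2017): "Discontinued study therapy due to an AE prior to the Early Clinical Response assessment".
- **Protocol v2.0, section 17.2.3.1** (27-OCT-2015): "Discontinued study therapy due to an AE and received alternative antibacterial treatment for CABP prior to the Early Clinical Response assessment".
- **Protocol v1.0, section 17.2.3.1**, now superseded: "Discontinued study therapy due to an AE prior to Early Clinical Response assessment".

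SAP Section 7, which is there to record departures from the protocol, reads in full: "The expanded microITT population was added and selected analyses are conducted in this population".

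Three further texts decide how missing assessments interact with the rule:

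- Protocol v2.0, section 22.15: "if any data field needed to determine the response is missing the subject will be assigned an Indeterminate response".
- SAP 8.3 applies its missing-data rule "unless the subject is considered a Clinical Failure for another reason".
- The second sensitivity analysis in SAP 10.2 counts subjects "lost to follow up prior to having an Early Clinical Assessment or have missing data, as an Early Clinical Success".

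**The concern.** Two current documents give different definitions of the confirmatory endpoint. The response is programmed, so the SAP wording is what will be coded, and that wording departs from the approved protocol without saying so. A reader of either document alone would misstate the endpoint.

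The SAP is dated about 17 months after protocol v2.0. Elsewhere it uses v2.0 content, such as the sputum criterion of more than 25 polymorphonuclear cells per field and the revised Safety population. The failure criterion therefore looks like v1.0 text carried over unnoticed, though the documents cannot prove that.

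The choice of rule can move subjects between Success and Failure in the primary analysis, and between Success and Failure in the sensitivity analysis meant to test the handling of indeterminate responses. SAP 10.2 plans no analysis under the other rule.

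**Working it through.** **1. Classification under each text.** Take a subject who stops for an AE before the assessment, receives no alternative antibacterial and meets no other non-symptom failure criterion.

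| Symptom data at 72–120 h | Protocol v2.0 | SAP |
|---|---|---|
| Complete; at least 2 symptoms improved, none worse | Success | Failure |
| Complete; fewer than 2 improved, or any worse | Failure | Failure |
| Not complete: primary analysis | Indeterminate (non-success) | Failure (non-success) |
| Not complete: Indeterminate-as-Success analysis | Success | Failure |

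Only the first row changes the primary result. The last row changes the sensitivity analysis, because SAP 8.3 takes subjects who fail for another reason out of the missing-data rule.

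**2. Can the first row occur?** Yes. The EOT visit falls on the day of the last dose or within 2 days after it, and symptoms are scored there. A subject whose last dose is the 48-hour infusion can have that visit up to about 96 hours, inside the window. SAP 8.6 uses the latest complete assessment in the window, so a stop on Day 4 or 5 can also precede it.

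**3. The plan's own figure.** Inputs from SAP 5.1.1: 750 subjects, 375 per arm, 79% in both arms, margin 10%, 1-sided alpha 0.025. Farrington-Manning power is Φ[(0.10 − 1.96·s0)/s1].

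- Restricted rates at a difference of −0.10 are 0.7316 and 0.8316.
- s0 = √[(0.7316·0.2684 + 0.8316·0.1684)/375] = 0.02995.
- s1 = √(2·0.79·0.21/375) = 0.02975.
- Power = Φ(1.388) = 91.7%, which reproduces the stated 92%.

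The stated power does not depend on the AE rule.

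**4. Effect of one subject.** 1/375 = 0.267 points on the difference. For scale, the interval half-width is 1.96·0.02975 = 5.83 points.

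**5. Effect on the lower limit.** This is the unstratified Miettinen-Nurminen 95% limit, solved from the equation in SAP 10.1. Moxifloxacin is held at 296/375 (79% of 375).

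| Omadacycline successes | Difference (points) | Lower limit (points) |
|---|---|---|
| 296 | 0.00 | -5.86 |
| 295 | -0.27 | -6.14 |
| 294 | -0.53 | -6.41 |
| 293 | -0.80 | -6.69 |
| 282 | -3.73 | -9.75 (non-inferior) |
| 281 | -4.00 | -10.03 (not shown) |

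From equal rates, losing the conclusion takes a net loss of 296 − 281 = 15 omadacycline successes. If the net loss falls on moxifloxacin, the limit moves the other way. If both arms lose the same number, the difference does not change.

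**6. How many subjects?** The documents give no rate of AE discontinuation before the assessment. The nearest figure is in protocol section 9.1, for a Phase 2 skin-infection study: "Premature discontinuation of treatment due to an AE was very infrequent, occurring in 0.9% and 1.9% of omadacycline and linezolid-treated subjects, respectively". Applied to 375 subjects, 0.009·375 = 3.4 and 0.019·375 = 7.1. These cover the whole course, in another indication and against another comparator. Only some of those subjects would stop before the assessment, go without alternative treatment and still improve. The net imbalance of 1 to 3 subjects used here is an assumption.

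**The case against.** The strongest reply is that the effect is too small to call for mandatory correction.

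- Losing the conclusion from equal rates takes 15 net reclassifications. The Phase 2 rates imply about 3 to 7 AE discontinuations per arm over the whole course, before any narrowing. Protocol 9.1 also reports no drug-related AE discontinuations among Phase 1 subjects given multiple doses.
- The qualifying group is narrow. AE stoppers who received alternative treatment for CABP before the assessment fail under both texts. If only the EOT and PTE visits take place, a subject who stops on Day 1 will generally have no assessment inside the window and is a non-success under both.
- The SAP must be approved before database lock, so the rule is not chosen after unblinding.
- SAP 8.3 already implies how an AE stopper without an assessment is treated in the sensitivity analysis, so the SAP is consistent within itself.

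All of this stands as far as size and opportunity for bias go, and the SAP needs no separate restatement of its missing-data rule. None of it removes the conflict. Approval before lock fixes which rule is used, but the programmed primary endpoint would still differ from the protocol without a declaration. The affected subject is uncommon but possible, and how many there are in each arm is unknown.

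**Conclusion.** The concern holds. The documents classify the same subject differently on the primary endpoint, no other section restores the protocol v2.0 condition, and SAP Section 7 is silent. This is a conflict between two current texts. The amendment summary serves only to show that the protocol wording was changed deliberately.

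The numerical effect is probably small: 0.27 to 0.80 points on the difference for an assumed net imbalance of 1 to 3 subjects, in a direction that cannot be known in advance. This rests on 375 per arm and 79% success in both arms. It would change the non-inferiority conclusion only in a borderline result. The sample size and stated power are unaffected.

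The case for correcting it before lock rests on its being the definition of the confirmatory endpoint. This review takes no position on which rule is right.

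**What to change.** Before database lock, reconcile protocol section 17.2.3.1 and SAP 5.2.1 so that one definition governs both. The sponsor can align the SAP criterion with protocol v2.0. Alternatively, it can keep the SAP rule, amend the protocol and declare the rule in SAP Section 7.

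Whichever rule is chosen, report Early Clinical Response under the other one as a named sensitivity analysis in SAP 10.2, with the number of reclassified subjects by arm.

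The cost is one edited criterion, one line in Section 7 or a protocol amendment, one derivation flag and one table. No new data are needed.

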5.2.2 Secondary Efficacy Outcomes

5.2.2.1 Investigators Assessment of Clinical Response

The investigator will make an assessment of Clinical Response at the EOT and PTE Visits, based on the definitions below. The secondary efficacy outcome is the overall assessment of clinical response at PTE (derived from the investigator assessments at the EOT and PTE Visits) in the ITT and CE-PTE populations as defined in [Table 3](#).

EOT Visit

At the EOT Visit (on the calendar day of, or within 2 days following the last dose of test article), the investigator will indicate the clinical status of the infection under study as detailed below.

Clinical Success: the subject is alive and the infection is sufficiently resolved such that further antibacterial therapy is not needed. These subjects may have some residual findings related to infection (ie, cough) requiring ancillary (ie, non-antibiotic) treatment (eg, expectorant). In order for the subject to be considered a Clinical Success at EOT, the subject may not meet any criteria for Clinical Failure or Indeterminate at EOT.

Clinical Failure: the subject requires alternative antibacterial treatment for CABP prior to EOT related to either (a) progression or development of new symptoms to CABP or (b) development of infectious complications of CABP (eg, empyema, lung abscess) or (c) subject developed an AE that required discontinuation of study therapy prior to the EOT. Other reasons for clinical failure are:

- Subject is receiving antibacterial therapy that may be effective for the infection under study for a different infection from the one under study.
- Death prior to EOT.

Indeterminate: the clinical response to test article could not be adequately inferred due to:

- Subjects were not seen for EOT evaluation because they withdrew consent, were lost to follow-up, other reason (specify).
- Other specified reason.

PTE Visit

At the PTE Visit (5 to 10 days after the subject's last day of study therapy) the investigator will indicate one of the following outcomes relating to the primary infection under study:

Clinical Success: survival after completion of a test article regimen without receiving any systemic antibacterial therapy other than test article, resolution of signs and symptoms of the infection present at Screening with no new symptoms or complications attributable to CABP and no need for further antibacterial therapy.

Clinical Failure: the subject requires alternative antibacterial treatment for CABP prior to PTE related to either (a) progression or development of new symptoms of CABP or (b) development of infectious complications of CABP (eg, empyema, lung abscess). Other reasons for clinical failure are:

- The subject is receiving antibiotics that may be effective for the infection under study for a different infection from the one under study.
- Death prior to PTE.

Indeterminate: the clinical response to test article could not be adequately inferred due to:

- Subjects were not seen for PTE evaluation because they withdrew consent, were lost to follow-up, other (specify).
- Other specified reason.

Overall Clinical Response at PTE (based on the investigator's assessment) is determined as follows from the investigator's assessments at the EOT and PTE Visits:

Table 3. Investigator's Assessment of Clinical Response

EOT Visit	PTE Visit	Overall Assessment of Clinical Response at PTE Visit
Success	Success	Success
Success	Failure	Failure
Success	Indeterminate	Indeterminate
Failure	Success	Failure
Failure	Failure	Failure
Failure	Indeterminate	Failure
Indeterminate	Success	Indeterminate
Indeterminate	Failure	Failure
Indeterminate	Indeterminate	Indeterminate

Abbreviations: EOT = end of treatment; PTE = post-therapy evaluation.

For the ITT population, the proportion of ITT subjects with a Clinical Success is defined using the following formula (where the denominator adds to the total number of subjects in the ITT population):

Number of subjects with Clinical Success

(Number of subjects with Clinical Success + Number of subjects with a Clinical Failure + Number of subjects with an Indeterminate response)

By definition, subjects in the CE-EOT and CE-PTE populations cannot have an Indeterminate response. Thus, for the CE-EOT and CE-PTE populations, the proportion of subjects with a Clinical Success is defined using the following formula:

Number of subjects with Clinical Success

(Number of subjects with Clinical Success + Number of subjects with a Clinical Failure)

